9.5 Consent

Stages 2 and 3:

Stage 2 and 3 participants will be able to contact the research team to answer any questions they have before providing consent to participate in this study (using contact details provided in the recruitment email and information shared in staff/team meetings). At this time they will also be provided with a PISCF, and complete the screening questions (as outlined above in the *screening* section). They will have a one-week period to consider their participation and provide consent. This timeframe was considered sufficient whilst preventing delays in the completion of the study as both Stages 2 and 3 are required to inform subsequent stages and thus the development of the rapid-response falls risk assessment and management service tool. If they then decide to participate, they will be asked to sign and complete the consent portion of the PISCF (paper-based or electronic) and return it to the research team prior to data collection either by emailing it to the researchers or returning it to the researchers' office based at HammondCare (in person or the internal mail system).

Stage 4:

Consent from client participants will be obtain verbally by a HC@H clinical or client care manager who is not involved in the direct care of the client (Figure 2. HC@H client recruitment

and consent process). Verbal, informed consent will be obtained during a phone call to discuss the study and screen the client's eligibility, as a means of being able to deliver a rapid response virtual service (within 48 hours of client being identified as a potential participant for this study). Prior to this phone call, the PIS will be provided to the client by HC@H staff so the client has this to refer to during the phone call. This process will occur after the falls risk stratification algorithm developed in this study has been deployed by HC@H staff during routine care (as detailed above in the *recruitment* and *screening* sections). The confirmation of verbal consent by the client will be audio recorded, and then securely stored in the *verbal consent confirmation* folder. Consent will be reconfirmed by the client when they complete the online (or paper-based equivalent) survey by clicking the 'I agree, start survey' button at the bottom of the consent declaration page (first page) of the survey (this must be selected in order to start the survey).

HC@H staff and HammondCare Restorative Care Team AHPs that are potential participants in Stage 4 (as detailed above in the *recruitment* and *screening* sections) will be provided with a copy of the PIS and link to the survey in the invitation email they are sent. If they would like, they can speak to the research team and ask any questions before providing consent. If participants consent to be involved in this stage of the study they will click on the survey link in the invitation email and then be asked to click the 'I agree, start survey' button at the bottom of the consent declaration page of the survey (this must be selected in order to start the survey). The survey will remain open for two weeks after the last invitation email is sent. The research team felt this was ample time for all potential participants to consider their involvement in the study and complete the survey. Reminder emails will not be sent as the survey is anonymous so it would not be possible to check which potential participants required a reminder email.

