Across Stages 2-4 HammondCare staff and clients will be enrolled in this study. HammondCare staff can consent to be involved in multiple stages. The target sample sizes for each stage are:

Stage 2:

Based on current literature, the target sample size is 18 (two to three focus groups of six to eight participants per group).¹² Ideally the sample size will be evenly distributed across the two participant groups: nine HC@H managers (a mix of clinical and client care managers), and nine HammondCare Restorative Care Team AHPs (a mix of physiotherapists, occupational therapists, and exercise physiologists).

Stage 3:

Based on other interview and survey studies, the target sample size is 22.¹² To ensure both components of the rapid-response falls risk assessment and management service tool are equally reviewed the sample size will be evenly split to include 11 HC@H staff (a mix of care workers, and clinical and client care managers) and 11 HammondCare Restorative Care Team AHPs (a mix of physiotherapists, occupational therapists, and exercise physiologists).

Stage 4:

The client target sample size is 13 HC@H community aged care clients, based on an anticipated referral rate of one per week (determined by staff feedback) over a three-month period. Potentially not all participants will require a virtual AHP falls risk assessment (dependent on the outcome of the falls risk stratification algorithm). To ensure sufficient data is collected for both components of the rapid-response falls risk assessment and management service tool a minimum of 50% of participants will need to have completed both the falls risk stratification algorithm and virtual AHP falls risk assessment. Therefore, recruitment will continue beyond the target sample size of 13 until the 50% minimum for completion of both components of the rapid-response falls risk assessment and management service tool is reached.

The staff target sample size is 13, based on recruitment of at least one member of staff per client participant (i.e. based on the falls risk stratification algorithm outcome for each client participant, a virtual AHP falls risk assessment may/ may not be indicated).

9. Selection and Withdrawal of Subjects

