HC@H staff and HammondCare Restorative Care Team AHPs that assist in the provision of the falls risk stratification algorithm or virtual AHP falls risk assessment (respectively) will be identified through review of the associated documentation within the clinical notes of Stage 4 client participants by a member of the research team. They will then be invited to participate in Stage 4 via a staff recruitment email sent via HC@H/HammondCare Restorative Care Team senior managers, independent of the research team. This email will include information about this stage of the study, the PIS, a link to the anonymous online survey, and the contact details of the research team to allow potential participants to ask further questions. The email will detail the steps the potential participant needs to follow if they would like to consent to participate in

this stage of the study (click on survey link, read the consent declaration [first page on weblink before starting survey], click the 'I agree, start survey' button at the bottom of the PIS page).

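### Anonymity does not rule out a blanket reminder for the Stage 4 staff survey, and the staff target of 13 has no allowance for non-response or for staff who serve several clients

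*Protocol*

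**What the plan says.** Section 9.5 (Consent, Stage 4) describes one invitation e-mail with a link to an anonymous online survey, which closes two weeks after the last invitation goes out. It then states "Reminder emails will not be sent as the survey is anonymous", and explains that the team could not check which invitees needed one.

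Section 9.3 (Recruitment Strategy, Stage 4) explains how the invitees are found. The staff who used the algorithm and the AHPs who did the virtual assessment "will be identified through review of the associated documentation within the clinical notes of Stage 4 client participants". It continues: "They will then be invited to participate in Stage 4 via a staff recruitment email sent via HC@H/HammondCare Restorative Care Team senior managers".

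Section 8 (Sample Size, Stage 4) gives the numbers. For clients: "The client target sample size is 13 HC@H community aged care clients, based on an anticipated referral rate of one per week", "over a three-month period". For staff: "The staff target sample size is 13, based on recruitment of at least one member of staff per client participant". It also requires that "a minimum of 50% of participants will need to have completed both the falls risk stratification algorithm and virtual AHP falls risk assessment", and says that "recruitment will continue beyond the target sample size of 13 until the 50% minimum" is reached.

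Section 10 (Treatment of Subjects) has each staff participant complete one survey, at the end of the pilot.

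**The concern.** The reason given does not support the rule. Not knowing who has replied prevents a message to non-responders only. It does not prevent the same message going to everyone on a list that already exists.

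The target makes this worth correcting. Thirteen staff at one per client works only if 13 different people serve the 13 clients and all of them reply, or if enough AHPs are added to the pool to make up the losses. The protocol says nothing about how many people it expects to invite or what share it expects to answer.

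At stake is the first research question in section 4, whether staff and AHPs find the tool suitable. Of the Stage 4 data sources listed in section 7 (clinical records, staff survey, client experience survey), only the staff survey records staff views after real use. With so few invitees, a handful of lost replies could leave one staff group thinly represented.

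**Working it through.** **The rule against its reason.** Section 9.5 needs to know who has responded only if the reminder is selective. Section 9.3 supplies a complete invitee list and a sending channel. A reminder to the whole list uses both and reveals nothing about who has replied.

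**The protocol's own figures (section 8).**
- Clients: 1 referral per week × about 13 weeks = 13. Reproduced.
- Staff: 1 per client × 13 clients = 13. Reproduced. No term for non-response or repeated staff appears.

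**Number invited (not stated; derived here).** Assume one HC@H staff member per client, all different; exactly the 50% minimum assessed; and a different AHP for each assessed client.
- Minimum with both components: 0.5 × 13 = 6.5, rounded up to 7.
- Pool: 13 + 7 = 20.
- Required response: 13 / 20 = 65%.

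The pool can move either way.
- *Smaller:* the same person may serve several clients. Section 9.3 draws the HC@H staff who help with client recruitment from Stages 2 and 3, whose targets are 9 managers and 11 HC@H staff. That is at most 9 + 11 = 20 people, fewer if some join both stages, so repeats are plausible.
- *Larger:* if all 13 clients are assessed, the pool is 13 + 13 = 26. If recruitment runs on to, say, 22 clients with 11 assessed, it is 22 + 11 = 33.

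**Chance of at least 13 replies.** The response rate is an assumption. With independent replies, the chance is the upper tail P(X ≥ 13) for X ~ Binomial(pool, rate).

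| Pool | Rate needed (13/pool) | 50% | 60% | 70% | 80% |
|---|---|---|---|---|---|
| 13 | 100% | <0.01 | <0.01 | 0.01 | 0.05 |
| 16 | 81% | 0.01 | 0.07 | 0.25 | 0.60 |
| 20 | 65% | 0.13 | 0.42 | 0.77 | 0.97 |
| 26 | 50% | 0.58 | 0.89 | 0.99 | 1.00 |
| 33 | 39% | 0.92 | 0.99 | 1.00 | 1.00 |

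With 20 invitees, the chance reaches one half at a response rate of about 62% and 80% at about 71%. The result depends almost wholly on two quantities that the protocol does not give.

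**The case against.** A reader might infer that the target is unlikely to be met, that the lack of reminders would be the cause, or that the pool cannot exceed 20 or 26. The documents support none of these.

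- *Unlikely to be met.* This needs both a pool size and a response rate, and neither is stated. With 20 invitees, a miss is more likely than not only below about 62% response; at 80% the chance of success is 0.97.
- *Caused by the missing reminder.* No response rate with or without reminders is given, so no shortfall can be attributed to it. Nor do the documents say that responders would be the more engaged users.
- *A ceiling of 20 or 26.* The 50% is a floor, client recruitment may pass 13, and section 4 allows the study to be extended.

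Other points also limit the finding. The two weeks run from the last invitation, so anyone invited earlier has longer. Staff views are also sought in the Stage 2 focus groups (target 18) and the Stage 3 interviews (target 22), although before the pilot. Section 14 plans only thematic and descriptive analysis, so no test or decision rule rests on 13 replies.

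The remedy has drawbacks too. Reminders sent through managers may feel like pressure, and an anonymous survey may collect duplicates that are hard to detect. These are real but small, and neutral wording deals with most of both. None of these points rescues the stated reason for having no reminders.

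**Conclusion.** The point holds in a limited form. Ruling out every reminder because the survey is anonymous is faulty reasoning: anonymity excludes targeted reminders only. Separately, the staff target of 13 contains no allowance for non-response or for one person serving several clients. It would need 65% response if 20 different people were invited, 81% if 16 and 50% if 26.

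The figure of 20 rests on 13 clients, one different HC@H staff member for each, exactly 7 assessed, and a different AHP for each of those. Whether the target would be missed cannot be determined from the protocol. Because the survey is descriptive, this is a cheap improvement and not a threat to the study's validity.

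**What to change.** In section 9.5, replace the sentence on reminders with text such as:

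> *One or two reminders will be e-mailed to every invitee, through the same senior managers, before the survey closes. Each will state that participation is voluntary, and that anyone who has already responded should ignore the message and not submit again.*

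Add to section 14 that the number of survey responses will be reported over the number of staff invited. The denominator is already available from the invitation list.

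Do not write a fixed pool range into section 8; the protocol gives no basis for one.

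The cost is one or two extra e-mails and two sentences of text. The downside is a small risk of duplicate entries, and of perceived pressure because the messages come through managers; the wording above is meant to limit both. The survey stays anonymous.

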9.6 Withdrawal of Consent or Participant

All participants in Stages 2 and 3, and HC@H client participants in Stage 4 will have the opportunity to withdraw their consent and data during this study up until the completion of data analysis. Once data has been collated in the analysis stage and group findings produced, the research team will no longer be able to withdraw a participant's individual data.

HC@H staff and HammondCare Restorative Care Team AHP participants in Stage 4 can withdraw their consent at any time during completion of the online survey by closing the survey before submitting. However, once it has been submitted they will not be able to withdraw their responses as the survey is anonymous.

It is not anticipated that involvement in this study will cause psychological distress. However, if a participant is observed to be distressed by their involvement in this study, the research activity will be ceased, and they will be given the opportunity to withdraw from this study. If HC@H staff and HammondCare Restorative Care Team AHP participants withdraw from this study they will be encouraged to contact their direct manager (e.g. regional lead or service manager) to arrange suitable physical or psychological support as needed (as per routine guidelines already in place to support HammondCare staff). If a HC@H client participant withdraws from this study they will be referred back to their HC@H clinical manager to then pursue the usual care pathway and any additional support required.

10. Treatment of Subjects

Stage 2:

Two to three focus groups will be conducted at Stage 2 (dependent on recruitment rates). Each participant will only have to attend one focus group. The focus groups are expected to run up to one hour (dependent on depth of discussion generated at the time). They will be conducted

online via Microsoft Teams during regular work hours (which the relevant HammondCare team will be reimbursed for) and audio recorded to support data transcription.

Stage 3:

Participants will be asked to work through real-world case scenarios using either the falls risk stratification algorithm (HC@H staff) or the comprehensive set of evidence-based falls risk assessments and interventions (HammondCare Restorative Care Team AHPs) on their own during regular work hours (which the relevant HammondCare team will be reimbursed for). They will then participate in an interview with a member of the research team to discuss this process and the component of the rapid-response falls risk assessment and management service tool they reviewed. The interview will be conducted online via Microsoft Teams during regular work hours (which the relevant HammondCare team will be reimbursed for) and audio recorded to support data transcription. Both activities during this stage (real-world case scenarios and interview) are expected to take approximately 30 minutes each, and only have to be completed once by each participant.

Stage 4:

HC@H staff will use the falls risk stratification algorithm to identify clients at increased falls risk during routine visits to clients as part of their HC@H service, taking up to 15 minutes. When clients consent to participate in a virtual AHP falls risk assessment, it will be conducted by HammondCare Restorative Care Team AHPs during regular work hours using a suitable device. The assessment is expected to take approximately 60 minutes. Time taken by staff to complete each components of the rapid-response falls risk assessment and management service tool will be reimbursed to the relevant HammondCare team. **The virtual service will be at no cost to the client.**

Once the virtual AHP falls risk assessment has been completed the AHP will liaise with the client's HC@H clinical or client care (as appropriate) manager about the recommended next steps. Potential options may include a virtually delivered falls program, a face-to-face AHP visit, liaison with GP or other usual care, which are all currently available services from HammondCare and are not the subject of this research (which is focussed on the development and pilot of the falls risk stratification algorithm and the virtual AHP falls risk assessment).

HC@H staff and HammondCare Restorative Care Team AHP participants will complete one anonymous survey using the online platform Qualtrics at the end of the pilot stage. HC@H client participants will complete one online PREM survey (via the Qualtrics platform) after their participation in Stage 4 (i.e. after completing either the falls risk stratification algorithm or the virtual AHP falls risk assessment). All surveys will take up to 15 minutes to complete. HC@H clients will be supported by HC@H staff as required to access and complete the online PREM survey (if needed/preferred an alternative paper version will be provided).

10.1 Trial Intervention

The trial intervention that will be piloted during Stage 4 will be developed in earlier stages (Stages 1-3) of the study, therefore it is not possible to detail specific components of the assessment intervention. However, both components of the rapid-response falls risk assessment and management service tool will be evidence-based on existing falls-related tools and best practice guidelines (i.e. neither component of the tool will be a new stand-alone development rather take a 'best of breed' approach). They will be developed based on existing

evidence of safety and efficacy, including consideration of tools most suitable for virtual assessments. The rapid-response falls risk assessment and management service tool will be administered by HC@H staff (falls risk stratification algorithm component) and HammondCare Restorative Care Team AHPs (virtual AHP falls risk assessment component), all of whom will receive training on the relevant component of the tool prior to Stage 4.

Following the virtual AHP falls risk assessment, the AHP will liaise with the client's HC@H clinical or client care (as appropriate) manager about their recommendations, which may include a virtually delivered falls program, a face-to-face AHP visit, liaison with GP or other usual care (all of which are currently available services from HammondCare and are not the subject of this research).

NOTE: For clients who are **not identified as being at risk of falls**, or who may have been identified as being at risk of falls but who **do not have the required connectivity** for a virtual assessment, or **who chose not to participate** in the study, these clients **will receive usual care** by HC@H (which may variously include standard referral to allied health, liaison with the client's GP, liaison with family members, review by a HC@H clinical care manager).

11. Safety and Monitoring

11.1 Assessment of Safety Event Report Forms

Safety reporting and monitoring will be in accordance with the HammondCare Institutional Research Governance Framework in accordance with the National Health and Medical Research Council's Management of Data and Information in Research: A guide supporting the Australian Code for the Responsible Conduct of Research (2019). Safety reports will be assessed on the seriousness, causality, and expectedness of the event to the trial treatment(s), intervention(s), investigational medical product(s), investigational medical device(s). The following are known and expected adverse effects, harms, risks or discomforts associated with trial procedures, treatments or interventions.

a) Known Adverse Effects

Nil

b) Known Harms, Risks or Discomforts

A fall

Physical exertion or discomfort

NOTE: The falls risk stratification algorithm and virtual AHP falls risk assessment will be conducted with the client's HC@H manager or care worker present, they will be closely monitored for any distress, inability to fully participate, or potential safety risk (e.g. a fall). They pose no greater risk than an AHP falls risk assessment conducted face-to-face.

11.2 Adverse Events or Adverse Reactions

Adverse events (AE) are considered any untoward medical occurrence in a patient or clinical trial participant administered the intervention, which does not necessarily have a causal relationship with this treatment.

Adverse Reactions (AR) are considered untoward and unintended responses to the trial intervention related to any intervention procedures.

AEs and ARs are assessed using the safety monitoring flow chart. Those classified as "not serious" are assessed by the qualified physician/medical expert specified in section 2 of the protocol. The Qualified Physician cannot delegate this responsibility to other research personnel.

Adverse event reports must be reported to the Coordinating Principal Investigator and the HammondCare Research Governance Committee within 48 hours. All adverse event reports must be recorded in HammondCare's Riskman database (an incident, hazard, near Miss, and feedback reporting database).

11.3 Serious Adverse Events

Serious Adverse Events (SAEs) that result in or lead to one or more of the following and the event is **not related** to the trial intervention:

- The death of a trial participant.
- A life-threatening illness or injury involving a trial participant.
- A participant's permanent impairment of body structure or body function.
- In-patient or prolonged hospitalisation (not for a pre-existing condition or an elective surgery) of a trial participant.
- Medical or surgical intervention to prevent life-threatening illness or injury or permanent impairment to a body structure or function of a trial participant.
- Fetal distress, fetal death or congenital abnormality or birth defect.

SAE reports are classified following the safety assessment flowchart and are assessed by Sponsors Independent Medical specified in section 2 of the protocol. The Sponsors Independent Medical cannot delegate this responsibility to other research personnel. SAE reports are reported to the Coordinating Principal Investigator and the HammondCare Research Governance Committee within 48 hours of the event occurring for multicentre clinical trials. SAR reports must be recorded in HammondCare's Riskman database (an incident, hazard, near Miss, and feedback reporting database).

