9.2 Exclusion Criteria

Stage 2:

Study group	Exclusion criteria
HC@H managers	
 • Participants that do not meet the inclusion criteria above. • Work outside of New South Wales (NSW), Australian Capital Territory (ACT), and Victoria.
HammondCare Restorative Care Team AHPs	
 • Participants that do not meet the inclusion criteria above. • AHPs other than those specified in the inclusion criteria. • Work outside of New South Wales (NSW), Australian Capital Territory (ACT), and Victoria.

Stage 3:

HC@H staff	
 • Participants that do not meet the inclusion criteria above. • Work outside of New South Wales (NSW), Australian Capital Territory (ACT), and Victoria.
HammondCare Restorative Care Team AHPs	
 • Participants that do not meet the inclusion criteria above. • AHPs other than those specified in the inclusion criteria. • Work outside of New South Wales (NSW), Australian Capital Territory (ACT), and Victoria.

Stage 4:

HC@H clients	
 • Participants that do not meet the inclusion criteria above. • Reside outside of New South Wales (NSW), Australian Capital Territory (ACT), and Victoria. • Insufficient English proficiency that prevents involvement in the virtual AHP falls risk assessment or survey. • Cognitive impairment that prevents their ability to provide informed consent. • Identified as at risk of falls and requires same day/urgent attention/referral as part of their usual care (e.g. urgent GP review due to a syncopal episode, same day review in the Emergency Department due to suspected head injury or fracture).
HC@H staff	
 • Participants that do not meet the inclusion criteria above. • Work outside of New South Wales (NSW), Australian Capital Territory (ACT), and Victoria.
HammondCare Restorative Care Team AHPs	
 • Participants that do not meet the inclusion criteria above. • AHPs other than those specified in the inclusion criteria. • Work outside of New South Wales (NSW), Australian Capital Territory (ACT), and Victoria.

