9.3 Recruitment Strategy

Stages 2 and 3:

Stage 2 and 3 participants will be invited to be involved in this study through recruitment emails sent to HC@H staff and HammondCare Restorative Care Team AHPs via HC@H and HammondCare Restorative Care Team senior managers respectively, independent of the research team. Information on this study will also be provided to senior managers from within both the HC@H team and the HammondCare Restorative Care Team so it can be shared via internal team communications (e.g. staff/team meetings). Study information will include contact details of the research team to allow potential participants to ask further questions.

In addition for Stage 3, at the end of the Stage 2 focus groups participants will be provided with information on Stage 3 and invited to participate in the subsequent stage (review of the rapid-response falls risk assessment and management service tool and interview).

Stage 4:

HC@H staff (care workers, and clinical and client care managers) involved in Stages 2 and 3 of this study will be engaged to assist with recruitment of HC@H clients for Stage 4. They will receive training on the use of the falls risk stratification algorithm prior to recruitment. For instance, when the HC@H staff member observes a deterioration in the client's mobility or function during routine care, or is concerned that the client may be at an increased risk of falls (e.g. sustained a recent fall or near miss) they will deploy the falls risk stratification algorithm developed in this study. They will also ask the client if a HC@H clinical or client care manager who is not involved in their direct care can phone them to discuss participating in this study (Figure 2. HC@H client recruitment and consent process).

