11.4 Serious Adverse Reactions

A Serious Adverse Reactions (SAR) is an SAE that is **related** to the trial intervention. SAR reports are classified following the safety assessment flowchart and are assessed by Sponsors Independent Medical specified in section 2 of the protocol. The sponsors independent medical expert must determine whether the SAR was expected or unexpected. The Sponsors Independent Medical cannot delegate this responsibility to other research personnel.

a) Expected Serious Adverse Reaction

A serious adverse reaction by its nature, incidence, severity, or outcome is anticipated and identified in the current version of the intervention safety information are classified as a SAR report. SAR reports are reported to the Coordinating Principal Investigator within 48 hours for multicentre clinical trials. Serious Adverse Reaction reports must be recorded in HammondCare's Riskman database (an incident, hazard, near Miss, and feedback reporting database).

b) Suspected Unexpected Serious Adverse Reaction (SUSAR)

A serious adverse reaction by its nature, incidence, severity, or outcome is unanticipated and not identified in the interventions instructions for use or safety information are classified as a SUSAR.

Fatal or life-threatening Australian SUSAR reports are reported to the Coordinating Principal Investigator, the sponsor's delegate, the HammondCare Research Governance Committee, and the approving HREC within 7 calendar days after being made aware of the case follow up information reported within a further 8 calendar days.

All other Australian SUSAR reports are to be reported to the Coordinating Principal Investigator, the sponsor's delegate, the HammondCare Research Governance Committee, and the approving HREC within 15 calendar days after being made aware of the case follow up information reported within a further 8 calendar days. SUSAR reports must be recorded in HammondCare's Riskman database (an incident, hazard, near Miss, and feedback reporting database).

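### Section 11.3 exempts any hospitalisation for a pre-existing condition from the seriousness criterion, without limiting this to planned admissions or unchanged conditions (minor)

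*Protocol*

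**What the plan says.** Section 11.3 lists six outcomes that make an event serious. The hospitalisation outcome reads "In-patient or prolonged hospitalisation (not for a pre-existing condition or an elective surgery) of a trial participant". The protocol does not define a pre-existing condition. Two neighbouring outcomes carry no such exemption: "A life-threatening illness or injury involving a trial participant" and "Medical or surgical intervention to prevent life-threatening illness or injury or permanent impairment to a body structure or function of a trial participant".

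Section 9.1 sets the age of Stage 4 clients at 65 or older. Under section 9.3 they are approached, for instance, "when the HC@H staff member observes a deterioration in the client's mobility or function during routine care", or when staff have another concern about falls. Section 9.2 excludes a client who is "Identified as at risk of falls and requires same day/urgent attention/referral as part of their usual care". Section 11.1 names two known harms: a fall, and "Physical exertion or discomfort".

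Section 11.4 builds the next category on section 11.3: "A Serious Adverse Reactions (SAR) is an SAE that is related to the trial intervention". Section 11.3, however, introduces its own list as covering events that are not related to the intervention.

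**The concern.** Seriousness definitions often leave out admissions that were already arranged, because these say nothing about what happened during the trial. This exemption goes further. The word elective attaches only to surgery, so the exemption for a pre-existing condition also covers emergency admissions for worsening.

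That matters in this population. Many Stage 4 clients come to notice because something has already deteriorated, so the condition of interest predates participation. Clients who need urgent attention at entry are excluded, so a later unplanned admission for the same problem would normally be a change from the state at entry. Exertion is a named harm, and it could plausibly act by aggravating existing disease. The exemption therefore falls on one route by which the assessment could do harm, and it sorts admissions by cause before anyone has judged relatedness.

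**Working it through.** No arithmetic applies: the protocol states no figure on this point and the question is one of wording. The check sets the clauses side by side and follows an event through them.

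1. **Scope of the exemption.** It has two limbs joined by *or*: a pre-existing condition, and elective surgery. Only the second carries a word that implies planning. Nothing else in the protocol adds a limit to the first.

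2. **Hypothetical cases under the hospitalisation criterion alone.**
   - A client approached for declining mobility has an unplanned admission because the decline worsened: exempt, so not serious on this ground.
   - A client with known heart failure has an unplanned admission with breathlessness shortly after the virtual assessment: exempt in the same way.
   - A client is admitted with a new pneumonia: serious.
   - A client is admitted with a new fracture after a fall: not plainly a pre-existing condition, so serious on the natural reading.

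   The gap is therefore confined to worsening of something already there.

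3. **Other grounds.** One of the six criteria carries the exemption. Death, life-threatening illness or injury, permanent impairment, and intervention to prevent such outcomes still capture the first two cases if they are met. The sixth, fetal outcomes, is irrelevant to these clients.

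4. **What an exempt admission keeps.** Under section 11.2 it is an adverse event, or an adverse reaction if related. It is assessed by the qualified physician, who may not delegate. Adverse event reports go to the Coordinating Principal Investigator and the Research Governance Committee within 48 hours and into the incident database. Section 11.3 gives an SAE the same two recipients and the same 48 hours.

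5. **What it loses.** Section 11.3 sends SAEs to the sponsor's independent medical expert; an event classed as not serious does not go there. Section 11.4 admits only SAEs to the SAR category, and only SARs are judged expected or unexpected. A related and unexpected admission that was not fatal or life-threatening would otherwise reach the ethics committee and the sponsor's delegate within 15 calendar days as a SUSAR. Under section 11.8, single reports of non-serious events need not go to either body.

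6. **A second fault in the same chain.** Section 11.3 describes SAEs as events not related to the intervention, while section 11.4 defines a SAR as a related SAE. Taken literally together, no event can be a SAR. Step 5 follows the evident intent: seriousness first, relatedness second. The two sections need to say so.

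**The case against.** The strongest reply is that little reporting is lost. Step 4 bears this out: recipients and deadline are the same for an adverse event and an SAE, and a physician reviews both. Section 11.1 also asks for causality to be assessed in all safety reports. Because it lists exertion among known and expected harms, an admission from exertion might be judged an expected reaction, which has no SUSAR route anyway. Significant safety issues and urgent safety measures reach the ethics committee whatever the SAE class (sections 11.5 and 11.6), and a Trial Safety Committee reviews the safety information (section 11.8). All of this stands and keeps the point small. It does not restore the independent expert's review or the SUSAR route for an event that is related and unexpected. The routes in sections 11.5 and 11.6 depend on someone recognising a wider issue.

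An experienced assessor may read the exemption as meaning planned admissions only, and the safety flowchart, which is not in the text at hand, may say so. Even then section 11.3 should match, or assessors may classify the same admission differently.

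The objection that the SAR chain is already broken by the not-related wording is also fair. It is a reason to repair both clauses together, not to leave the exemption as it is.

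**Conclusion.** The point holds as a minor fault in a stated rule. Followed as written, section 11.3 classes an unplanned admission for worsening of a condition present at entry as not serious unless another criterion is met. This rests on the literal text and assumes that the flowchart adds no limit.

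Three stronger readings are not supported:

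- **That such admissions cannot be serious, or go unrecorded.** Only the hospitalisation criterion is affected, and the event remains a reportable adverse event.
- **That a number of missed events can be derived.** A reader might apply an assumed three-month admission risk to the target of 13 clients. In section 8, three months is the recruitment period at one referral a week, not each client's time under observation. The protocol states no safety follow-up of that length per client, no admission rate, and no share of admissions due to existing conditions. Participation itself is an algorithm of up to 15 minutes, for some clients an assessment of about 60 minutes, and one survey (section 10).
- **That a tested safety comparison is biased.** Section 11.1 asserts in a note that the procedures carry no more risk than a face-to-face assessment. The pilot has no comparator, and section 14 plans no analysis that tests this.

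**What to change.** Reword the criterion in section 11.3 along these lines: *In-patient or prolonged hospitalisation, except an admission planned before the falls risk stratification algorithm was first deployed with the client, and only if it is for a pre-existing condition that has not worsened or for elective surgery.*

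The anchor should be deployment of the algorithm, not consent. Section 9.5 places consent after deployment, so a consent anchor would still exempt an admission arranged between the two.

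In the same edit:

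- align the safety assessment flowchart with the new wording;
- remove the conflict between sections 11.3 and 11.4 by defining an SAE by seriousness alone and judging relatedness afterwards.

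The cost is a sentence, a change to the lead-in of section 11.3, a check of the flowchart, and possibly a few more SAE reports to assess. It changes a reporting definition and leaves clients' care untouched.
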